5.6 Handling of dropouts, missing data and outliers

Outliers will be included in summary tables and listings and will not be handled separately in any analyses. All collected data, even if not tabulated, will be listed. Generally, no imputation of data will be performed. However, when calculating statistics for PK plasma concentrations, concentrations under LLOQ will be replaced with LLOQ/2 if more than 50% of the values for a given time point are above LLOQ. Otherwise, no statistics will be calculated for that time point. For figures presenting individual PK concentrations, no imputation is performed for values under LLOQ. For imputation of PK plasma concentration below LLOQ with the purpose of calculating PK parameters, see Section 9.2.1.

Safety laboratory concentrations under LLOQ will be replaced with LLOQ/2 and concentrations over ULOQ will be replaced with ULOQ for the purpose of calculating descriptive statistics.

In case of missing start and stop times of AEs that cannot be investigated further, missing data will be imputed according to a worst-case scenario, i.e., start time will be imputed as the closest time point post first intake of IMP and end time as 23:59, resulting in the longest possible treatment emergent duration of the AE.

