6.1.2 Clinical experience

In a first-in-human (FIH) Phase 1 clinical trial, GZ17-6.02 was well tolerated when orally administered to oncology patients with solid tumours and lymphoma at a dose of [REDACTED] 375mg twice a day (daily dosage equivalent 750 mg).

[REDACTED]

[REDACTED]

[REDACTED]

Thus, there is clinical experience regarding GZ17-6.02 at higher doses and longer treatment duration than for the proposed topical trial.

[REDACTED]

[REDACTED]

[REDACTED] The PK analysis showed that all PK samples were below the detection limit.

Preliminary and blinded data showed that GZ21T has been generally well tolerated, without clinically significant findings regarding AEs, ECG, safety laboratory assessments, physical examinations and local tolerability findings.

[REDACTED]

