9.3 Number of participants

Part A: Approximately, 64 potential participants will be screened to achieve 32 randomised participants (4 cohorts, 8 participants per cohort randomised in a 6:2 ratio).

Part B: Approximately 18 potential participants will be screened to achieve up to 9 included participants.

For the replacement of participants who discontinue the trial, see Section 9.8.3.

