5 STATISTICAL AND ANALYTICAL PLANS

5.1 Sample size calculation and number of participants

No formal sample size calculation has been performed for this trial. The proposed sample size is considered sufficient to provide adequate information to meet the trial objectives.

Part A: Approximately 64 participants were planned to be screened to achieve 32 randomised participants (8 in each cohort).

Part B: Approximately 18 potential participants were planned to be screened to achieve up to 9 included participants, 3 subjects per cohort.

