5.2 Definition of analysis sets

The analysis sets defined for the trial are outlined in Table 4.

Table 4 Analysis sets

Analysis set	Definition	Comment	Use of analysis set
Full analysis set (FAS)	All enrolled participants who received IMP.	Participants will only receive 1 dose of IMP. Therefore, the phrase (as stated in the CTP) “at least 1 dose of” before “IMP” is removed from the definitions to minimise confusion.	Part A and Part B: Safety endpoints and description of trial population.
Pharmacokinetic analysis set (PKAS)	All randomised participants in Part A who received IMP and provided an evaluable plasma concentration profile, and who have no AEs or protocol deviations judged to affect the PK analysis. Individual PK values may be excluded from the analysis.		Part A: PK endpoints.

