10.2.3 Secondary endpoints (Part A)

10.2.3.1 Pharmacokinetic analysis (Part A)

Table PC 1 Plasma concentrations – Part A (Pharmacokinetic analysis set)

Assessment (unit)		Assessment timepoint			
[PARAMETER 1] (unit)	[Assessment timepoint 1]	n/BLQ	xx/xx	xx/xx	xx/xx
		Mean (SD)	x.xx (x.xx)	x.xx (x.xx)	x.xx (x.xx)
		Median (Min, Max)	x.xx (x.x, x.x)	x.xx (x.x, x.x)	x.xx (x.x, x.x)
		Geometric Mean (geo CV%)	x.xxx (x.x%)	x.xxx (x.x%)	x.xxx (x.x%)
	[Assessment timepoint 2]	n/BLQ	xx/xx	xx/xx	xx/xx
		Mean (SD)	x.xx (x.xx)	x.xx (x.xx)	x.xx (x.xx)
		Median (Min, Max)	x.xx (x.x, x.x)	x.xx (x.x, x.x)	x.xx (x.x, x.x)
		Geometric Mean (geo CV%)	x.xxx (x.x%)	x.xxx (x.x%)	x.xxx (x.x%)

Data based on [population]. BSA: Body surface area. LLOQ is xx (unit). See listing 16.2.5-1 for a per participant LLOQ summary. n: Number of observations. BLQ: Below lower limit of quantification. SD: Standard deviation. CV%: Coefficient of variation described as percentage. Geo CV%: Geometric coefficient of variation described as percentage calculated using log-transformed standard deviation. NC: Not calculated - number of evaluable observations less than 3 or more than half of the observations are BLQ. NA: Not available - no evaluable observations. SAS program: [PROGRAM NAME].sas.

Dataset version: ADXX YYYY-MM-DDTHH:MM:SS. Run by: [USERNAME] YYYY-MM-DDTHH:MM:SS. EDC data extracted: YYYY-MM-DDTHH:MM:SS.

Table PP 1 PK parameters – Part A (Pharmacokinetic analysis set)

Assessment (unit)		Assessment timepoint			
Tmax (unit)	n	xx	xx	xx	xx
	Median (Min, Max)	x.xx (x.x, x.x)	x.xx (x.x, x.x)	x.xx (x.x, x.x)	x.xx (x.x, x.x)

Assessment (unit)					
Cmax (unit)	n	xx	xx	xx	xx
	Mean (SD)	x.xx (x.xx)	x.xx (x.xx)	x.xx (x.xx)	x.xx (x.xx)
	Median (Min, Max)	x.xx (x.x, x.x)	x.xx (x.x, x.x)	x.xx (x.x, x.x)	x.xx (x.x, x.x)
	Geometric Mean (geo CV%)	x.xxx (x.x%)	x.xxx (x.x%)	x.xxx (x.x%)	x.xxx (x.x%)
AUC0-last (unit)	n	xx	xx	xx	xx
	Mean (SD)	x.xx (x.xx)	x.xx (x.xx)	x.xx (x.xx)	x.xx (x.xx)
	Median (Min, Max)	x.xx (x.x, x.x)	x.xx (x.x, x.x)	x.xx (x.x, x.x)	x.xx (x.x, x.x)
	Geometric Mean (geo CV%)	x.xxx (x.x%)	x.xxx (x.x%)	x.xxx (x.x%)	x.xxx (x.x%)
AUC0-inf (unit)	n	xx	xx	xx	xx
	Mean (SD)	x.xx (x.xx)	x.xx (x.xx)	x.xx (x.xx)	x.xx (x.xx)
	Median (Min, Max)	x.xx (x.x, x.x)	x.xx (x.x, x.x)	x.xx (x.x, x.x)	x.xx (x.x, x.x)
	Geometric Mean (geo CV%)	x.xxx (x.x%)	x.xxx (x.x%)	x.xxx (x.x%)	x.xxx (x.x%)
T1/2 (unit)	n	xx	xx	xx	xx
	Mean (SD)	x.xx (x.xx)	x.xx (x.xx)	x.xx (x.xx)	x.xx (x.xx)

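### SAP Section 5.6 and the Table PC 1 footnote part ways when exactly half the plasma values are below LLOQ, and Figures PC 1 and PC 2 leave out values that Section 5.6 imputes

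*SAP*

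**What the plan says.** SAP Section 5.6 sets the rule for summarising plasma concentrations: "concentrations under LLOQ will be replaced with LLOQ/2 if more than 50% of the values for a given time point are above LLOQ". It continues: "Otherwise, no statistics will be calculated for that time point". The same section switches imputation off for figures of individual concentrations, and only for those.

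The footnote to Table PC 1 in SAP Section 10.2.3.1 gives its own condition for an empty cell: "NC: Not calculated - number of evaluable observations less than 3 or more than half of the observations are BLQ". The same sentence appears under Table PP 1, the table of PK parameters.

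Figures PC 1 and PC 2 (SAP Section 10.3.1.1) are titled as geometric mean plasma concentrations over time. Their footnotes state that values under LLOQ are left out of the figure.

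On numbers, Protocol Section 9.3 gives "4 cohorts, 8 participants per cohort randomised in a 6:2 ratio". Table PC 1 is based on the PK analysis set, which SAP Section 5.2 defines as "All randomised participants in Part A who received IMP and provided an evaluable plasma concentration profile" and without adverse events or deviations judged to affect the PK analysis.

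**The concern.** Section 5.6 and the Table PC 1 footnote both use a strict inequality, facing opposite ways. One needs more than half of the values above LLOQ before it calculates; the other needs more than half below LLOQ before it withholds. Exactly half falls between them. No passage settles a tie or says which text prevails. Six active participants is an even number, so the tie can occur in a complete cohort.

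The figures raise a second question that does not depend on a tie. A geometric mean plotted after dropping the low values is not the statistic that Section 5.6 defines, so table and figure can show different means for the same data.

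Plasma concentration is the first-listed secondary endpoint. What is at stake is whether its summary output is fixed in advance or depends on which sentence the programmer follows.

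**Working it through.** The SAP has no figure of its own to reproduce here, so the check compares the rules and then sizes the gap.

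**Inputs**
- Active participants per Part A cohort: 8 × 6/8 = 6 (Protocol Section 9.3).
- Calculate if the share above LLOQ is greater than 50%, otherwise not (SAP Section 5.6).
- Not calculated if fewer than 3 are evaluable or the share below LLOQ is greater than 50% (Table PC 1 footnote).
- Probability p that a value is quantifiable: not in the documents, so a range is used.
- Assumed: the 50% is judged within each cohort's active group. The Table PC 1 column headings are redacted, so columns of six are inferred from the 6:2 ratio.

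**Step 1. Every split of six**

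| Below LLOQ | Above LLOQ | Section 5.6 | Table PC 1 footnote |
|---|---|---|---|
| 0, 1, 2 | 100%, 83%, 67% | calculated | calculated |
| 3 | 50% | no statistics | NC conditions not met |
| 4, 5, 6 | 33%, 17%, 0% | no statistics | NC |

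The minimum of three does not resolve the tie. At three of six there are 6 assayed and 3 quantifiable values, and neither count is below 3. With an odd number analysed, such as five, there is no tie.

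**Step 2. Chance of the tie, per cohort and time point**

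With independent participants and a common p within the cohort, P(3 of 6) = C(6,3) p³(1−p)³ = 20 p³(1−p)³.

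| p | Calculation | P(3 of 6) |
|---|---|---|
| 0 | 0 | 0 |
| 0.05 | 20 × 0.000125 × 0.857 | 0.2% |
| 0.1 | 20 × 0.001 × 0.729 | 1.5% |
| 0.2 | 20 × 0.008 × 0.512 | 8.2% |
| 0.3 | 20 × 0.027 × 0.343 | 18.5% |
| 0.5 | 20 × 0.125 × 0.125 | 31.3% |

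On where p may lie, Protocol Section 6.1.2 reports: "The PK analysis showed that all PK samples were below the detection limit". The surrounding text is redacted, so which samples are meant is not visible. Protocol Section 8.3.4 also describes very low systemic exposure in minipigs. Both point to small p.

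**Step 3. Table against figure**

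Let b of n values be below LLOQ, and let G be the geometric mean of the quantifiable ones.
- Under Section 5.6, when it calculates: G^((n−b)/n) × (LLOQ/2)^(b/n).
- Under the figure footnote: G.
- Ratio, figure to table: (2G/LLOQ)^(b/n).

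Since G is at least LLOQ, the ratio is at least 2^(b/n), which exceeds 1 whenever b is 1 or more. For n = 6:
- b = 1: at least 2^(1/6) = 1.12.
- b = 2: at least 2^(1/3) = 1.26.
- b = 2 with G assumed to be 2 × LLOQ: 4^(1/3) = 1.59. The table shows 2/1.59 = 1.26 × LLOQ and the figure 2.00 × LLOQ.
- b = 3, 4 or 5: Section 5.6 gives no statistic, while the figure footnote still allows a point from three or fewer participants.

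**The case against.** The strongest reply is that Section 5.6 is the operative rule and the footnote only explains a code in a mock table that still holds placeholders. The footnote does not order a calculation at a tie. The same sentence stands under Table PP 1, where it hardly fits parameters such as Tmax or half-life, which suggests template text and not a considered second rule. This is fair, and it is why the remedy keeps Section 5.6. It does not remove the mismatch: at three of six a programmer working from the shell finds no condition for printing NC, and the SAP does not say that the text overrides the shell.

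Several stronger readings are tempting, but the documents do not support them.
- A reader might infer that the footnote would print a definite value at a tie, such as 1.0 × LLOQ for three values at 2 × LLOQ and three at LLOQ/2. The footnote contains no imputation rule, and Section 5.6 allows LLOQ/2 only above 50%, so that figure borrows an imputation that the tie does not permit.
- A reader might combine cohorts: 1 − (1 − 0.185)⁴ = 56% for a tie in at least one of four at p = 0.3. That needs one common p across cohorts that differ in application area or site, and a p well above what Protocol Section 6.1.2 suggests.
- A reader might fear for comparisons between cohorts or for dose escalation. No between-cohort test is planned, PK parameters have their own rule for values below LLOQ in SAP Section 9.2.1, and the internal safety review committee reviews plasma data cohort by cohort (Protocol Section 8.3.5).

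The minimum of three evaluable observations is an extra table condition and not part of the conflict. In a full cohort Section 5.6 already needs at least four quantifiable values.

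On the figures, one could say that their footnotes apply the no-imputation clause of Section 5.6. That clause covers individual concentrations, which are Figures PC 3 and PC 4. Figures PC 1 and PC 2 show means, and means are statistics under the first part of the rule. This reading rests on titles and footnotes; the template graphs were not available for the check.

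It also stands that Table PC 1 prints the number below LLOQ and Listing 16.2.5-1 gives every concentration, so nothing is hidden from a careful reader.

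**Conclusion.** The point holds as a minor inconsistency in descriptive PK output. In a full active cohort the text and the table footnote disagree at one split only, three of six. How often that would occur depends on a quantifiable probability that the documents do not give. It never occurs if all samples are below LLOQ, it is rare if few are quantifiable, and it becomes common only if quantifiability is moderate. The available information favours the first two. Exclusions that leave an odd number analysed would remove the tie.

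The figure footnotes are the wider discrepancy. They contradict Section 5.6 at any time point where some but not all values are below LLOQ. The plotted mean is then higher than the one in Table PC 1, or appears where the table has none.

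Neither issue touches the primary safety endpoints, the PK parameters or the escalation decisions.

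**What to change.** Keep the Section 5.6 rule and bring the shells into line with it:
- Table PC 1 footnote: *NC: fewer than 3 evaluable observations, or 50% or more of the observations BLQ.*
- Table PP 1 footnote: align the BLQ clause with this wording or delete it.
- Figures PC 1 and PC 2: replace the exclusion footnote with the Section 5.6 rule, that is, LLOQ/2 for values under LLOQ where more than 50% are above LLOQ, and no point otherwise. Figures PC 3 and PC 4 stay as they are.

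The cost is a few words in footnotes, best settled before database lock and unblinding, with no new data. The small downside is that a three-of-six time point shows NC; the individual values remain in Listing 16.2.5-1.

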6 CHANGES FROM THE CLINICAL TRIAL PROTOCOL

Changes to the planned analyses and the timing of these are summarised in Table 5.

Table 5 Changes in the planned statistical analyses

Change category	Timing of change	Description of change	Reason for change
Change in the SAP compared to the CTP	Prior to DBL	
A minor change has been made to the phrasing of the definitions for FAS and PKAS. This change does not affect whether participants are included in the analysis sets or not. See Table 4 for details.
 
In section 9.1.1, definitely related AEs has been added to the definition of causally related AEs, which is missing from sections 11.3.1.11 and 17.6.1 of the CTP.
 
Frequency tables for safety laboratory interpretations have been added.
 
The overall/total column has been removed from all safety tabulations, except for AEs and LTs.
	To minimise confusion. “Definitely related” was missing from the AE definitions in sections 11.3.1.11 and 17.6.1 of the CTP To provide a better overview of the safety laboratory data. Redundant information.

7 CLINICAL DATABASE PROCESSING

7.1 General information

The clinical database is processed and generated according to The Clinical Data Interchange Standards Consortium (CDISC). CDISC is a Standard Developing Organization which develops and publishes standards to normalise the structure of clinical trial data and thereby simplify submissions to and reviews by authorities such as the Food and Drug Administration (FDA).

The CDISC standards for clinical studies are the Trial Data Tabulation Model (SDTM) and the Analysis Data Model (ADaM). The trial data will be structured into a database model reflecting the SDTM and will be compliant to SDTM Implementation Guide (SDTM-IG) version 3.3. The data used for statistical analysis will be structured to reflect the ADaM and be compliant to ADaM Implementation Guide (ADaM-IG) version 1.3.

Data values are collected according to, or mapped into, controlled terminology codelists defined by CDISC, whenever possible. The codelists are updated quarterly at CTC and the latest version available at trial start will be used. As per default, controlled terminology codelists will be used in all tables, listings, and figures. Custom codelists for test or parameter names will be used if applicable upon Sponsor's request, to align with protocol texts, or to adhere to other standard naming conventions (e.g., PK parameter name "Tmax" will be used instead of the CDISC term "Time of CMAX"). These custom codelists will be mapped in the "Parameter Name" field in the ADaM structure, while the CT will be kept in the SDTM predecessor fields to provide traceability back to CDISC codelists.

7.1.1 CDISC Compliance

The trial database will be CDISC compliant which means that the clinical database will be processed and generated according to CDISC standard. The database will be validated against SDTM and ADaM Validation rules using Pinnacle 21.

The following CDISC documentation will be generated:

- SDTM Data Definition Specification (also referred to as a Define -XML)
 - Define-XML transmits metadata that describes any tabular dataset structure and supports the interchange of dataset metadata for clinical research applications in a machine-readable format.
- ADaM Data Definition Specification (also referred to as a Define -XML)
 - Define-XML transmits metadata that describes any tabular dataset structure and supports the interchange of dataset metadata for clinical research applications in a machine-readable format.
- Annotated Electronic Case Report Form (eCRF)
 - Links the data collection fields used to capture trial data to the corresponding variables in the trial database. It enables the user to understand how the trial data were collected and to trace back from trial analysis results to the origin where it was collected.
- SDTM Reviewers' Guide
 - Intended to provide additional context and act as a single point of orientation for the SDTM datasets.
- ADaM Reviewers' Guide
 - Provides regulatory agency reviewers an orientation to the submitted analysis data in a consistent way and usable format.

7.2 Database modeling of trial design

The trial design is mapped to a SDTM trial design model containing the following structural components:

[figure not shown]
EPOCH: An interval of time in the planned conduct of a trial. An epoch is associated with a purpose (e.g., screening, randomisation, treatment, follow-up), and applies across all arms of the trial. Trial epochs follow a controlled terminology to represent the different trial parts (e.g., SCREENING, TREATMENT [X], FOLLOW-UP)

[figure not shown]
ELEMENT: Building blocks used to build up the entire trial length for all participants. Information on ELEMENTs is extracted from the trial design and schedule of events in the protocol. ELEMENTs are defined to span the entire trial without gaps. One EPOCH may contain one or several ELEMENTs. All ELEMENTs must have transition rules in accordance with the protocol to determine start and end.

ARM: Participants are allocated to trial arms depending on the trial design, either by randomisation or other allocation processes defined in the trial protocol. ARMs are defined as the total number of planned ways a participant can go through the trial (unique combination of trial ELEMENTs). All ARMs must contain a unique sequence of ELEMENTs.

VISIT: Trial visits are defined as planned timepoints during the trial where trial data is collected. A visit can be performed in clinic, by off-site contact with trial personnel (phone call, video conference or similar), or by participant initiated recordings of data. The visit schedule is extracted from protocol and eCRF design.

A schematic representation of the SDTM trial design is presented in Figure 2. Replace the figure below with a relevant version for the trial.

8 STATISTICAL DELIVERABLES

The following items will be delivered:

- Statistical analyses, summary tables, listings and figures as described under Section 10.
- Clinical trial database delivered as a SAS-export file and Excel files.

9 STATISTICAL METHODOLOGY

All collected data will be listed by part, participant, cohort and treatment, and, where applicable, by assessment time.

The data for participants receiving placebo will be presented pooled across groups.

Details on statistical analyses and descriptive summaries are specified below.

All statistical analyses and descriptive summaries will be performed using SAS version 9.4 (SAS institute, Cary, NC).

PK parameters will be calculated by Non-Compartmental Analysis (NCA) using the software Phoenix WinNonlin® version 8.3 (Certara, U.S.A).

9.1 Analysis of the primary endpoints

9.1.1 *Adverse events*

An overview of all AEs, including SAEs, intensity, relationship to IMP, and deaths will be presented by part, cohort treatment, and overall. The incidence of AEs and SAEs will be summarised by SOC and PT by treatment, cohort and overall. A summary of any treatment-related (probably/possibly/definitely related) AEs will be summarised by SOC and PT and by treatment, cohort and overall if considered appropriate.

9.1.2 *Local tolerability*

An overview of all local tolerability reactions including maximum intensity grade per local tolerability reaction will be presented by part, cohort, treatment, and overall. Intensity grade for each local tolerability reaction will also be presented by cohort, treatment, and overall using a frequency table. Changes from baseline in intensity grade at each time point will be summarised in a shift table.

9.1.3 *Vital signs*

Vital signs will be summarised by treatment and cohort, and by assessment time point. Data will be presented with absolute and percent change from baseline. Vital signs data (blood pressure and pulse) for eligibility (screening) in Part B will only be listed.

9.1.4 *Electrocardiogram*

All ECGs will be categorised as "normal", "abnormal, not clinically significant", or "abnormal, clinically significant" (as judged by the Investigator) and summarised by treatment and cohort, and by assessment time point using frequency tables. Changes over time will be presented using a shift table if considered appropriate. All measured ECG values will be summarised by treatment, cohort and overall, and assessment timepoint with absolute and percent change from baseline. ECG data for eligibility (screening) in Part B will only be listed.

9.1.5 *Safety laboratory*

Safety laboratory data will be summarised by treatment and cohort, and by assessment time point with absolute and percent change from baseline.

All safety laboratory measurements will be categorised as "normal", "abnormal, not clinically significant", or "abnormal, clinically significant" (as judged by the Investigator) and

summarised by treatment and cohort, and by assessment time point using frequency tables. Safety laboratory data for eligibility (screening) in Part B will only be listed.

